11.1.1.2. Sample Size

A sample size of 200 leads (185 required for analysis plus 15 for attrition) is required to evaluate Primary Safety Endpoint. This sample size was calculated using the normal approximation to the binomial and confirmed via Monte Carlo simulations employing Kaplan-Meier methodology, using SAS version 9.4 with the following assumptions:

- Expected performance = 98%
- Performance goal = 93%
- Expected attrition/missing data = 7.5%
- One-sided significance level = 2.5%
- Power = 90%

The sample size for the INGEVITY+ Study is determined by this endpoint.

11.1.1.3. Statistical Methods

Data from all implanted or attempted leads at the time of endpoint analysis will be eligible for inclusion in the endpoint analysis.

The lead-related complication-free rate from date of implant (or date of attempt, for leads attempted but not implanted) through 91 days post-implant will be calculated using Kaplan-Meier methodology. The 97.5% one-sided lower pointwise confidence limit of the complication-free rate will be calculated via log-log methodology for all eligible leads contributing to the analysis and compared to the performance goal of 93%. If the lower confidence limit exceeds 93%, the null hypothesis will be rejected.

Each lead's exact follow-up time in the 91-day post-implant period will be included in the analysis via Kaplan-Meier methodology. The leads that fail to reach 91 days of follow-up (without experiencing an endpoint event prior to their end of follow-up in the period) will be censored at the time of their end of follow-up in the period. Because non-informative censoring cannot be assumed for these leads, a tipping point analysis will be performed to determine the potential effects these censored leads could have on the results if full information on each lead was present. The tipping point analysis will assign each lead that was censored prior to 91 days as either having or not having an endpoint event. All possible combinations of these leads' data will be evaluated along with the actual observed data to find the point, if any, at which the endpoint is failed. An exact binomial test will be performed for the tipping point analysis.

11.1.2. Primary Efficacy Endpoint

The Primary Efficacy Endpoint will confirm the percent of leads with an adequate mean INGEVITY+ Pacing Capture Threshold (PCT) measurement. A lead with an adequate mean INGEVITY+ PCT measurement will be referred to as a Pacing Capture Threshold Responder.

11.1.2.1. Hypotheses

H_0 : Pacing Capture Threshold Responders at 3-month visit $\leq 80\%$

H_A : Pacing Capture Threshold Responders at 3-month visit $> 80\%$,

where a Responder is defined by a mean PCT at 3-month visit ≤ 2 V.

The PCT measurements will be taken using a 0.4 ms pulse width. The performance goal of 80% aligns with current performance goals accepted by the FDA for leadless pacemakers and responder rates from previous RV lead studies.

11.1.2.2. Sample Size

A total of 57 measurements (3-month [contact] ms) are required to sufficiently power the Primary Efficacy Endpoint. The following assumptions were used to calculate the sample size:

- Performance goal = 80%
- Expected rate = 95%
- One-sided significance level = 2.5%
- Power = 90%

The sample size for this study was not determined by this endpoint.

11.1.2.3. Statistical Methods

All INGEVITY+ leads with a PCT measurement taken at the 3-month visit (with a 0.4 ms pulse width) will be included in the endpoint evaluation. The number of responders (PCT at 3-month visit ≤ 2 V) divided by the total number of INGEVITY+ leads included in the endpoint evaluation will be calculated. The one-sided 2.5% binomial exact lower confidence limit will be calculated and compared to the performance goal of 80%. If the lower confidence limit exceeds 80%, the null hypothesis will be rejected.

To assess the potential impact missing data could have had on the analysis results, a tipping point analysis will be conducted that will include all implanted INGEVITY+ leads. The tipping point analysis will assign each lead with missing data as either being a PCT responder or a PCT non-responder. All possible combinations of these leads' data will be evaluated along with the actual observed data to find the point, if any, at which the endpoint is failed.

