Procedure/Assessment*	Enrollment ≤ 30 days prior to Implant	Index Procedure Day 0 ¹	Post- procedure/ Prehospital Discharge 3-72 hours ¹	Follow-up Visits		
				1 Month (30 ± 7 Days) ¹ Clinic Visit	3 Month (91+31 Days) ¹ Clinic Visit	Additional Visit
Informed consent process, including informed consent signature date	X	-	-	-	-	-
Demographics	X	-	-	-	-	-
Physical assessment, including weight and height	X	-	-	-	-	-
Medical history	X	-	-	-	-	-
Implant Questionnaire	-	X	-	-	-	-
PSA measurements for all leads	-	X	-	-	-	-
PA and lateral chest X-ray and/or fluoroscopic image of lead distal tip fixation	-	X		-	-	-
Cardiovascular Medications	X	-	-	-	X	-
IPG lead measurements for all leads	-	X	X	X	X	O / X**
Adverse events assessment/reporting	X	X	X	X	X	X
Device deficiency assessment/reporting		X	X	X	X	X
Protocol deviation	X	X	X	X	X	X

X = Required; - = Not required/Not Applicable; O = Optional

¹ Clock starts after end of implant procedure, day of implant is day 0, and pocket closure is hour 0

* See Table 10-3 in Section 10.12 for full source requirements

**Required if there is a lead-related AE or device deficiency, otherwise optional

10.2. *Study Candidate Screening*

For the INGEVITY+ Study, physician investigators are responsible for screening all potential patients and selecting those who are appropriate for study inclusion. The patients selected for participation should be from the investigator's general patient population with an indication for implantation of a Boston Scientific dual-chamber pacemaker or CRT-P system according to the product labeling (Physician's Technical Manual).

10.3. *Informed Consent*

Patients who appear to meet all of the inclusion criteria and none of the exclusion criteria and agree to participate in the INGEVITY+ Study must give written informed consent in a form approved by the investigational center's IRB prior to study participation and data collection. The Investigator is responsible for ensuring that Informed Consent is obtained prior to any study-required procedure and/or testing, or data collection. Patients who complete the informed consent process and sign and date the informed consent for the INGEVITY+ Study will be considered enrolled in the study at the point of executing an ICF.

10.4. *Enrollment Visit [≤ 30 days prior to Implant]*

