10.8.1. Lead Measurements with IPG

Lead measurements, including pacing thresholds, sensed amplitudes, and pacing impedances are required at the 3-month visit for all implanted leads. Pacing and sensing evaluation using the IPG (either pacemaker or CRT-P) must be performed. Lead measurements are required unless the testing is inhibited by a subject condition (subject has no intrinsic rhythm or subject is in atrial fibrillation).

If the visit is performed in-clinic during the INGEVITY+ Study, pacing threshold measurements will be collected in a standard manual fashion in bipolar electrode configuration. At least two (2) cardiac cycles at a given voltage level shall be obtained before stepping down to the next voltage level. A count of two (2) non-capture beats is required at a given voltage level to declare a loss of capture (LOC) for any of these tests. The threshold is defined as one voltage level above the level where two (2) non-captured beats are observed.

The following measurements are to be taken utilizing the IPG to ensure adequate sensing and pacing function of all leads:

- Intrinsic amplitude (mV)
- Voltage pacing capture threshold in the bipolar mode lead configuration (V, at 0.4 ms pulse width).
- Lead impedance (Ω)

If a remote visit with LATITUDE lead measurements is performed see section 10.10

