Assessment of pregnancy for women of childbearing potential: method of assessment per physician discretion	Retain at site
Documentation of: 
 Demographics: age at implant, gender, race, ethnicity Indication for implant Cardiovascular medications Subject's height and weight Arrhythmia history Cardiac disease history 	Retain at site
Implant details regarding IPG, leads, and accessories used or signed Implant Technical Source Form	Retain at site
Printout of PSA measurements and ECG strip showing loss of capture or signed Implant Technical Source Form	Retain at site
Implant questionnaire	Retain at site
For in-clinic visits: Printout of IPG measurements and threshold results (device follow-up report and ECG programmer strip documenting LOC), for all lead pacing threshold tests	Retain at site
For remote visits: Appropriate LATITUDE report or page print of LATITUDE data or signed Technical Source Form for IPG measurements and threshold results	Retain at site
Time of pocket closure, to document time 0	Retain at site
Time of pre-discharge visit to document visit window	Retain at site
PA and lateral chest X-ray or fluoroscopic image of lead distal tip fixation, either from Implant or Pre-Discharge	Retain at site
Reportable Adverse Events, Device Deficiencies, and Protocol Deviations, if applicable	Retain at site
In the event of subject death: 
 Death narrative Relevant medical records Death certificate Autopsy report 	Submit one copy to Boston Scientific RM At [contact] or uploaded to the Rave Database Retain at site

Note: If thermal paper from the device programmer is used for source documentation, signed and dated photocopies or printed pdfs should be used instead, or the strips should be electronically saved.

11. Statistical Considerations

11.1. *Endpoints*

For an INGEVITY+ lead to be eligible to contribute to endpoint analyses, it must be the final lead implanted or attempted per chamber during the initial procedure. Therefore, each subject may contribute up to two total INGEVITY+ leads to the endpoint analyses – one each for the right atrium and right ventricle. See section 11.3.1 for specifics on the analysis sets used for each endpoint analysis.

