11.1.1. Primary Safety Endpoint: Lead-related Complication-Free Rate from 0 to 3 Months

Safety of the INGEVITY+ Leads will be confirmed by the lead-related complication-free rate (CFR) from lead implant through the three-month follow-up, based on complications that are related to the INGEVITY+ Lead. Lead-related complications are defined as lead-related adverse events resulting in permanent loss of pacing therapy, invasive intervention, injury, or death. Lead-related adverse events include, but are not limited to the following, based on the Advamed Industry Guidance for Uniform Reporting of Clinical Performance of Cardiac Rhythm Management of Pulse Generators and Leads¹, and in accordance with the FDA Guidance²:

- Cardiac perforation requiring surgical intervention
- Cardiac perforation not requiring surgical intervention
- Conductor fracture/ helix damage
- Lead dislodgment
- Failure to capture
- Oversensing
- Failure to sense (undersensing)
- Insulation breach
- Abnormal pacing impedance
- Extracardiac stimulation

Lead-related complications associated with attempted INGEVITY+ Lead implants will count toward this safety endpoint. Lead-related adverse events that are not a complication will be counted as a complication if intravenous (IV) drug therapy is necessary to treat the event. IV drug therapy that occurs concomitant but unrelated to the lead-related adverse event will not be counted as a lead-related complication. Complications involving an INGEVITY+ lead that occur as a result of a procedure unrelated to that INGEVITY+ lead will not count toward this safety endpoint. Two examples of this scenario are 1) an INGEVITY+ lead dislodgement resulting from an ablation procedure and 2) an RV INGEVITY+ lead dislodgement resulting from a repositioning of an RA lead (INGEVITY+ or other market-released).

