11.1.4.1. Hypotheses

The following hypotheses will be used to evaluate Effectiveness Endpoint 3 for each of the lead fixation types:

$$H_0: \text{Pacing impedance} \leq 300 \Omega, \text{ or Pacing impedance} \geq 1300 \Omega$$

$$H_a: 300 \Omega < \text{Pacing impedance} < 1300 \Omega$$

11.1.4.2. Sample Size for Secondary Effectiveness Endpoint 2

A sample size of 15 leads (13 required for analysis plus 2 for attrition) is required for Effectiveness Endpoint 3. This sample size was calculated using a one-sample t-test, using SAS version 9.4 with the following assumptions:

- Expected performance = $650 \pm 400 \Omega$
- Performance goals = 300Ω and 1300Ω
- Expected attrition/missing data = 10%
- One-sided significance level = 5%
- Power = 90%

Note that the sample size for the study is not determined by this endpoint.

11.1.4.3. Statistical Methods for Secondary Effectiveness Endpoint 2

All pacing impedance data collected at the three-month follow-up visit that is available at the time of analysis will be included in the endpoint analysis.

Two one-sided t-tests (TOST) will be performed, using an alpha equal to 5% for each test. If the TOST is deemed to be inappropriate based on the data, a data transformation or a non-parametric test will be performed. If both of the p-values for the two one-sided tests are less than 0.05, the null hypothesis will be rejected.

11.2. *Ancillary Analysis*

- Summary of turn count for all implanted and attempted leads
- Summary of the implant questionnaire including:
 - Lead handling
 - Lead maneuverability
- Summary of accessories used

- Summary of lead-related Adverse Events
- Summary of lead-related device deficiencies, including extension/retraction issues

11.3. ***General Statistical Methods***

11.3.1. **Analysis Sets**

For an INGEVITY+ lead to be eligible to contribute to endpoint analyses, it must be the final lead implanted or attempted per chamber during the initial procedure. Therefore, each subject may contribute up to two total INGEVITY+ leads to the endpoint analyses – one each for the right atrium and right ventricle. These leads will be called ‘endpoint leads’ in this section. The following analysis sets will be used for each endpoint.

Endpoint	Analysis Sets
Primary Safety Endpoint	All endpoint leads
Primary Efficacy Endpoint	All endpoint leads with 3-month visit PCT data
Secondary Efficacy Endpoint 1	All implanted endpoint leads with 3-month visit sensed amplitude measurements

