22.2. Definitions

Terms are defined in Table 22-2.

Table 22-2: Definitions

Term	Definition
Lead-related adverse event	
Lead-related adverse events include, but are not limited to the following, based on the Advamed Industry Guidance for Uniform Reporting of Clinical Performance of Cardiac Rhythm Management of Pulse Generators and Leads¹ and in accordance with the FDA Guidance²:
 
 • Cardiac perforation requiring surgical intervention • Cardiac perforation not requiring surgical intervention • Conductor fracture/ helix damage • Lead dislodgment • Failure to capture • Oversensing • Failure to sense (undersensing) • Insulation breach • Abnormal pacing impedance • Extracardiac stimulation
Lead-related complication	Lead-related complications are defined as lead-related adverse events resulting in permanent loss of pacing therapy, invasive intervention, injury or death.
Observation	An adverse event that was transient or reversible and corrected with non-invasive interventions, such as reprogramming or oral medications, or else resolved with no intervention or monitoring.
Pacing impedance	An assessment of the opposition to the flow of current by the pacing system; measured in ohms (Ω).
Pacing threshold	An assessment of the minimum electrical stimulation required to consistently initiate cardiac depolarization; measured in Volts (V).
Permanent Atrial Fibrillation (AF) ³	When a patient and clinician make a joint decision to stop further attempts to restore and/or maintain sinus rhythm.
Persistent AF ³	Continuous AF that is sustained > 7 days.
Sensed amplitude	An assessment of how well the lead senses the heart's intrinsic electrical activity; measured in millivolts (mV).
Source Data	All information in original records of clinical findings, observations, or other activities in a clinical investigation, necessary for the reconstruction and evaluation of the clinical study.
Source Document	Printed, optical or electronic document containing source data. Examples: Hospital records, laboratory notes, device accountability records, radiographs, records kept at the investigation site, and at the laboratories involved in the clinical study.

23. Bibliography

¹ Industry Guidance for Uniform Reporting of Clinical Performance of Cardiac Rhythm Management of Pulse Generators and Leads, (21 May 2009).

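### A lead removed before 3 months for documented failure to capture or elevated threshold leaves the primary efficacy denominator instead of counting as a non-responder; the effect is small but only raises the rate

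*Combined protocol and SAP*

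**What the plan says.** Section 11.1.2.1 tests whether more than 80% of leads are pacing capture threshold (PCT) responders at the 3-month visit, a responder having a mean PCT of 2 V or less. Section 11.1.2.3 sets the denominator: "All INGEVITY+ leads with a PCT measurement taken at the 3-month visit (with a 0.4 ms pulse width) will be included". The table in 11.3.1 agrees: "All endpoint leads with 3-month visit PCT data". The null hypothesis is rejected if the exact lower limit from these leads exceeds 80%.

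A lead placed at a later revision cannot take the place of the one removed. To be an endpoint lead, "it must be the final lead implanted or attempted per chamber during the initial procedure" (11.1, repeated in 11.3.1). Under 9.2, a subject whose lead is explanted is followed for about 30 days and may then be withdrawn. No section says how a lead removed for a threshold problem is scored for efficacy.

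Section 11.1.2.3 adds a tipping-point analysis covering every implanted INGEVITY+ lead: "The tipping point analysis will assign each lead with missing data as either being a PCT responder or a PCT non-responder", over all combinations. No decision is tied to its result.

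For the safety endpoint, 11.1.1 lists failure to capture among lead-related adverse events. It exempts complications "that occur as a result of a procedure unrelated to that INGEVITY+ lead will not count toward this safety endpoint".

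**The concern.** A lead taken out because it would not capture, or because its threshold had risen, has a known outcome on the property this endpoint measures. The plan handles it like a lead whose subject died or withdrew, that is, as unknown. The primary rate then describes leads still in place and tested at 3 months, not all implanted endpoint leads. Because the excluded leads are failures, the error runs in one direction, in the device's favour. At stake are how far the reported rate is overstated and whether a pass on the 80% goal could depend on it.

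**Working it through.** **Inputs.** Goal 80%, expected rate 95%, one-sided 2.5%, power 90%, 57 measurements (11.1.2.2). 200 leads, of which 185 are analysed and 15 allowed for attrition; expected complication-free rate 98% (11.1.1.2). Exact (Clopper-Pearson) lower limit (synopsis; 11.1.2.3). The number of threshold-related removals, k, is not in the documents, so k = 1, 2 and 4 are assumptions. The value 4 is every complication expected in 200 leads (2% × 200), treated as if each were a threshold-related removal.

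**The plan's own figure.** Normal approximation: n = [(1.960·√(0.80·0.20) + 1.282·√(0.95·0.05)) / 0.15]² = 50.2. With continuity correction: (50.2/4)·[1 + √(1 + 2/(50.2·0.15))]² = 56.7, rounded up to 57. The stated 57 reproduces.

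**Direction.** With x responders among n measured leads and k excluded failures, the plan reports x/n where counting them gives x/(n + k). For x and k above zero, the first is always larger.

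**Size at planned values.** 0.95 × 185 = 175.75, so x = 176. The exact one-sided 97.5% lower limit is the 0.025 quantile of Beta(x, N − x + 1), with N = 185 + k.

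| k counted as non-responders | Rate | Lower limit |
|---|---|---|
| 0 | 176/185 = 95.1% | 91.0% |
| 1 | 176/186 = 94.6% | 90.3% |
| 2 | 176/187 = 94.1% | 89.7% |
| 4 | 176/189 = 93.1% | 88.5% |
| 15 (whole attrition allowance) | 176/200 = 88.0% | 82.7% |
| 21 | 176/206 = 85.4% | 79.9% |

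Only the last row fails, and 21 exceeds the 15 leads allowed for attrition.

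**Where the decision could change.** The fewest responders that pass are 159 of 185 (limit 80.1%), 161 of 187 (80.3%) and 163 of 189 (80.5%). With k = 2, the two analyses disagree only at 159 or 160 responders among the 185 measured. With k = 4 they disagree at 159 to 162, that is 85.9% to 87.6%. The binomial probability of landing there is:

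| True measured rate | k = 2 | k = 4 |
|---|---|---|
| 95% | 0.0006% | 0.006% |
| 92% | 0.5% | 2.2% |
| 90% | 4.5% | 13% |
| 87% | 16% | 33% |

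**Error rate for the rate as the plan words it.** P(X ≥ 159 | n = 185, p = 0.80) = 2.3%, within the nominal 2.5%.

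All figures treat leads as independent, as the planned exact limit does, although a subject may contribute two.

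**The case against.** The strongest reply is that the plan already covers this. The tipping-point analysis takes in all implanted leads and every combination, so the case in which each removed lead is a failure will be reported. A failure to capture that leads to invasive intervention also counts in the safety endpoint, which is analysed on all endpoint leads. Measuring thresholds among leads tested at 3 months, and counting lead failures under safety, is a coherent division, and the hypothesis does refer to the 3-month visit. The 80% goal rests partly on responder rates from previous RV lead studies (11.1.2.1), and the documents do not say whether those studies counted removed leads. Finally, the present denominator is objective. The alternative depends on a recorded reason for lead loss, events are classified by the sponsor's safety group (19.1), and elevated threshold is not named in the 11.1.1 list.

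Much of this stands. It limits the size of the problem and argues for keeping the measured-leads rate in the report. It does not remove the point: the decision rests on the measured-leads limit alone, and the tipping-point analysis treats a documented failure as if its outcome were open.

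A reader might infer that the test's error rate is inflated, from 1.8% to 8.0%, by taking 200 implanted leads with a true rate of 80% and 4 failures excluded. The documents do not support that. The plan does not state an all-lead target, and for the rate it does state the error is 2.3%. The contrast also assumes that all other leads are measured, against the planned 7.5% attrition. Part of the rise is discreteness of the exact test, whose size at a constant 80% moves from 1.8% at 200 leads to 2.5% at 196. With 185 measured leads the same scenario (true measured rate 160/196 = 81.6%) gives 7.4% against 2.3%, still for a target the plan does not state. Nor is 4 a realistic count: 11.1.1 also lists perforation, dislodgment, oversensing, insulation breach and other events.

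**Conclusion.** The point holds as a minor one, worth considering. The deciding analysis drops leads already known to have failed on threshold or capture, and that can only raise the rate. At planned values the overstatement is 0.5 percentage points for one such lead (95.1% against 94.6%) and 2.0 points for four (95.1% against 93.1%), and the trial passes either way. With up to 4 such leads, a reversal needs 159 to 162 responders of 185, well below the expected 95%. It would be wrong to conclude that the planned test is invalid for its stated rate, or that missing leads go unexamined.

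The size rests on assumed counts of threshold-related removals, on 185 measured leads and on independence between leads. A lead that is repositioned and stays in place still has a 3-month PCT, so it is not affected.

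**What to change.** In 11.1.2.3 and 11.3.1:

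- Count as a non-responder in the primary analysis any implanted endpoint lead explanted, replaced or abandoned before the 3-month visit with documented failure to capture or elevated threshold as the reason. Except events caused by a procedure unrelated to that lead, following the exemption in 11.1.1.
- Fix the list of qualifying reasons before analysis.
- Hold these leads as non-responders in every tipping-point combination. Leave all other losses as missing there.
- Report the measured-leads-only rate as a sensitivity analysis, for comparability with the 80% goal.

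Cost: the rate becomes slightly less favourable, one event can count against both primary endpoints, and the result depends on the recorded reason for lead loss. Little new data should be needed. Lead-related adverse events are already reportable (17.1), and Table 10-1 marks lead measurements at additional visits as "Required if there is a lead-related AE or device deficiency, otherwise optional". The documents do not describe a dedicated field for the reason a lead was removed, so check that the adverse event form captures it. Section 11.4.6 allows a change made before analysis to be documented in the approved SAP; amending the protocol text as well would need IRB review (14.3).
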